
 
To describe the effect of nirmatrelvir/ritonavir on viral clearance for the treatment of COVID-19 in nonhospitalized symptomatic participants <math>\geq 12</math> years of age with COVID-19 who are immunocompromised.
 
	
 
Proportion of participants with SARS-CoV-2 RNA <math>< \text{LLOQ}</math> in plasma over time.
 
Proportion of participants with SARS-CoV-2 RNA level in NP swabs <math>< 2.0 \log_{10}</math> copies/mL at each study visit through Day 44.
 
Change from baseline in SARS-CoV-2 RNA level in NP swabs and in plasma over time.
 
Rebound in SARS-CoV-2 RNA level in NP swabs at follow up (ie, any study visit after end of treatment through Day 44) that is defined as a half (<math>0.5 \log_{10}</math> copies/mL) increase or greater in SARS-CoV-2 RNA level relative to end of treatment SARS-CoV-2 RNA level based on treatment regimen, with a follow-up viral RNA level <math>\geq 2.5 \log_{10}</math> copies/mL.
 
	
 
Not applicable.
 

 
To describe the safety and tolerability of nirmatrelvir/ritonavir
 
	
 
Incidence of TEAEs.
 
	
 
Not applicable.
 

Objectives	Endpoints	Estimands
for the treatment of COVID-19 in nonhospitalized symptomatic participants $\geq 12$ years of age with COVID-19 who are immunocompromised.	
 
Incidence of SAEs and AEs leading to discontinuations.
 
	

 
To describe the effect of nirmatrelvir/ritonavir on hospitalization and all-cause mortality in nonhospitalized symptomatic participants <math>\geq 12</math> years of age with COVID-19 who are immunocompromised.
 
	
 
Proportion of participants with COVID-19-related hospitalization >24 hours, or death from any cause through Day 28.
 
Proportion of participants with death (all cause) through Week 24.
 
	
 
Not applicable.
 

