### **In addition, the following inclusion criteria only apply to the additional population with rebound:**

5. Presenting with documented, symptomatic, COVID-19 rebound within 14 days following completion of an initial 5-day treatment course with nirmatrelvir/ritonavir.

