**Study Arms and Duration:**

Eligible participants for this study will be randomly assigned (1:1:1) to receive nirmatrelvir plus ritonavir orally q12h as specified in the table below.

Study Intervention(s)				
Intervention Name	Nirmatrelvir	Placebo for nirmatrelvir	Ritonavir	Placebo for ritonavir
Arm Name (group of participants receiving a specific treatment or no treatment)	nirmatrelvir/ritonavir	placebo	nirmatrelvir/ritonavir	placebo
Unit Dose Strength(s)	150 mg	0 mg	100 mg	0 mg
Route of Administration	Oral	Oral	Oral	Oral
Use	Experimental	Placebo	Experimental	Placebo
IMP or NIMP/AxMP	IMP	IMP	IMP	IMP

Study Arm(s)			
Arm Title	Nirmatrelvir/ritonavir 5-day	Nirmatrelvir/ritonavir 10-day	Nirmatrelvir/ritonavir 15-day
Arm Type	Experimental, placebo	Experimental, placebo	Experimental
Arm Description	Participants will receive nirmatrelvir/ritonavir 300 mg/100 mg (or 150 mg/100 mg for participants with eGFR $\geq$ 30 to <60 mL/min/1.73 m  or eCrCl $\geq$ 30 to <60 mL/min) q12h from Day 1 through Day 5 followed by placebo for nirmatrelvir/placebo for ritonavir q12h for Day 6 through Day 15.	Participants will receive nirmatrelvir/ritonavir 300 mg/100 mg (or 150 mg/100 mg for participants with eGFR $\geq$ 30 to <60 mL/min/1.73 m  or eCrCl $\geq$ 30 to <60 mL/min) q12h from Day 1 through Day 10 followed by placebo for nirmatrelvir/placebo for ritonavir q12h for Day 11 through Day 15.	Participants will receive nirmatrelvir/ritonavir 300 mg/100 mg (or 150 mg/100 mg for participants with eGFR $\geq$ 30 to <60 mL/min/1.73 m  or eCrCl $\geq$ 30 to <60 mL/min) q12h from Day 1 through Day 15.

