**Table 1. Study Schedule of Assessment**

Visit Identifier' Abbreviations used in this table may be found in Section 10.11.	Screening	Baseline (Day 1)	Day 5	Day 10	Day 15	Day 21	Day 28	Day 35	Day 44	LTF/U		ET (pilot to Day 44)	Notes
										Week 12	Week 24		
Visit Window	Day -1 to Day 1	0 days	bl:1 day	bl:1 day	±2 days	±2 days	±2 days	±3 days	±3 days	±1 days	±7 days	±5 days	
 
Screening procedures may be done from Day -1 to Day 1, and may be completed on the same calendar day as Baseline/Day 1 procedures. If screening and baseline visits are conducted on the same calendar day, assessments and procedures that are listed to occur at both visits only need to be completed once.
 

Study intervention dispensation		X	X	X									
 
Study intervention will be dispensed on Day 1, Day 5, and Day 10 (see Section 6.1.1).
 
Should eGFR or eCrCl (based on the point-of-care creatinine) on Day 5 or Day 10 warrant a dose modification, replacement study intervention will be dispensed on Day 5 or Day 10. See Section 10.7.1 for age specific kidney function calculations.
 
See Section 6.6.
 

Study intervention administration		Day 1 through Day 15											
 
Baseline assessments should be performed before administration of the first study intervention, except for PK sampling.
 
The first dose of study intervention will be administered to all participants on Day 1 during the in person visit. All subsequent doses of study intervention (ie, 29) will be self-administered (or administered to the participant by a legal guardian or caregiver). If only 1 dose of study intervention is administered on Day 1, study intervention administration should end on Day 16.
 
See Section 6.1.1.
 

Study Intervention Accountability													
Retrieval of unused study intervention and empty study intervention containers			X	X	X							X	
 
If the Day 15 visit is conducted prior to last dose of study intervention, empty study intervention containers and unused study intervention should be returned at the Day 21 visit.
 
See Section 6.5.
 

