### **2.2.1. Clinical Overview**

The safety and efficacy of a 5-day treatment with nirmatrelvir/ritonavir in adults was demonstrated in Study C4671005 (EPIC-HR, NCT094960202), which enrolled nonhospitalized symptomatic adults, including participants who were immunocompromised, with laboratory-confirmed diagnosis of SARS-CoV-2 infection with at least 1 risk factor for progression to severe disease and with a COVID-19 symptom onset of  $\leq 5$  days. In the analysis of the primary endpoint from all participants enrolled in Study C4671005, an 89% reduction in COVID-19-related hospitalization or death from any cause compared with placebo in participants treated within 3 days of symptom onset was observed. 0.72% of participants who received nirmatrelvir/ritonavir were hospitalized through Day 28 following randomization (5 of 697 hospitalized with no deaths), compared to 6.45% of participants who received placebo and were hospitalized or died (44 of 682 hospitalized with 9 subsequent deaths) ( $p < 0.001$ ). In a secondary endpoint, nirmatrelvir/ritonavir reduced the risk of hospitalization or death for any cause by 88% compared with placebo in participants treated within 5 days of symptom onset; 0.77% of patients who received nirmatrelvir/ritonavir were hospitalized through Day 28 following randomization (8 of 1039 hospitalized with no deaths) compared with 6.31% of patients who received placebo (66 of 1046 hospitalized with 12 subsequent deaths) ( $p < 0.001$ ). Treatment with nirmatrelvir/ritonavir was safe and well tolerated.

On 22 December 2021, the US FDA granted EUA to nirmatrelvir/ritonavir for the treatment of mild-to-moderate COVID-19 in adults and pediatric patients (12 years of age or older weighing  $\geq 40$  kg) who are at risk for progression to severe disease.

Refer to the IB for more details on studies, including clinical efficacy, safety, and PK results for completed and ongoing studies.

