#### **10.9.5. Inclusion Criteria for Additional Population With COVID-19 Rebound**

Inclusion Criterion #2: Confirmed SARS-CoV-2 infection as determined by RT-PCR or rapid antigen testing in any specimen collected within 24h prior to randomization and collected within 14 days after the completion of the initial 5-day treatment course of nirmatrelvir/ritonavir.

Note: RT-PCR is the preferred method; however, with evolving approaches to confirmation of SARS-CoV-2 infection, other molecular or antigen tests that detect viral RNA or protein are allowed. The test result must be available to confirm eligibility. Participants may be enrolled based on positive results of a rapid SARS-CoV-2 antigen test performed at screening.

Inclusion Criterion #5: Presenting with documented, symptomatic, COVID-19 rebound within 14 days following completion of an initial 5-day treatment course with nirmatrelvir/ritonavir, defined as:

1. Participants must have written documentation, such as electronic health record, medical record, or prescription receipt of treatment with nirmatrelvir/ritonavir (verbal assertion of treatment is not acceptable) with patient-reported 100% compliance (ie, completed a 5-day course of nirmatrelvir/ritonavir). They must have symptom alleviation or resolution in COVID-19 signs/symptoms followed by a worsening (rebound) of signs/symptoms after completing an initial 5-day course of nirmatrelvir/ritonavir based on the judgement of both the participant and investigator.
2. The onset of rebound in COVID-19 symptoms must occur within 14 days after the completion of the initial 5-day course of nirmatrelvir/ritonavir.
3. Onset of signs/symptoms attributable to rebound COVID-19 within 48 hours prior to randomization and  $\geq 1$  sign/symptom to COVID-19 present on the day of randomization.

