6.2.8. Incidence of SAEs and AEs leading to discontinuations

The incidence of SAEs and AEs leading to discontinuation will be summarized by treatment group using the safety analysis set.

6.2.9. Proportion of participants with COVID-19-related hospitalization >24 hours, or death from any cause through Day 28

The proportion of participants with COVID-19-related hospitalization >24 hours, or death from any cause through Day 28 will be summarized. The cumulative proportion of participants hospitalized for the treatment of COVID-19 or death during the first 28 days of the study will be estimated for each treatment group using the Kaplan-Meier method to take account of losses to follow-up and summarized graphically for each treatment group.

For participants without an event who complete the Day 28 assessment, they will be censored at Day 28. For participants without an event who discontinue or are lost to follow-up before the Day 28 assessment, they will be censored at the last known date in the study.

6.2.10. Proportion of participants with death (all cause) through Week 24

The proportion of participants who died from any cause through Week 24 will be analyzed using the method specified in Section 6.2.9 and summarized for each treatment group. KM plots for each treatment group will also be provided. Participants without an event will be censored at the last known date in the study.

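### The hospitalization-or-death composite stops at Day 28, leaving 23, 18 and 13 off-treatment days in the 5-, 10- and 15-day arms; report it through Day 44 as well

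*Protocol*

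**What the plan says.** Protocol Sections 1.1, 3 and 9.3.3 list the composite of COVID-19-related hospitalization for more than 24 "hours, or death from any cause through Day 28". SAP 6.2.9 estimates it by the Kaplan-Meier method in each arm: "For participants without an event who complete the Day 28 assessment, they will be censored at Day 28". SAP Appendix 1 also sets Day 28 as its latest censoring time. No later version of this composite is planned.

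The arms stop active drug at different times. The 15-day arm takes it "q12h from Day 1 through Day 15", while the other two switch to placebo after Day 5 or Day 10. If only one dose is taken on Day 1, "study intervention administration should end on Day 16".

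Other endpoints run longer. Virologic rebound is sought at "any study visit after end of treatment through Day 44". SAP 6.2.11 to 6.2.13 take COVID-19 hospitalization of any duration, ICU admission and ventilation or ECMO to Day 44 and to Week 24, although Appendix 1 gives Day 44 as the maximum censoring time for all three. All-cause death runs to Week 24.

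**The concern.** Protocol Section 4.3 justifies the longer courses by what happens after treatment: they may keep viral RNA from rising again once dosing stops. Whether a longer course prevents relapse-related illness or only moves it later is therefore central to the trial. A horizon fixed at Day 28 gives the 15-day arm ten fewer off-treatment days than the 5-day arm. If relapse follows the end of treatment by a similar interval whatever the duration, more of it falls beyond Day 28 in the longer arms. Their composite would then look lower with no event prevented.

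Day 28 is also the horizon of the earlier high-risk trial described in Protocol Section 2.2.1 ("0.72% of participants who received nirmatrelvir/ritonavir were hospitalized through Day 28 following randomization"). That trial tested a single 5-day course, so the problem of unequal treatment ends did not arise between active durations.

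**Working it through.** The documents give no expected rate, precision or event count for this composite, so there is no planned figure to reproduce. The check is calendar arithmetic plus an illustration on stated assumptions.

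**Off-treatment time** = horizon minus last active dose day (5, 10 or 15).
- To Day 28: 28−5 = 23, 28−10 = 18, 28−15 = 13 days.
- To Day 44: 39, 34 and 29 days.
- If dosing starts with a single dose, and assuming the last active dose shifts by one day in every arm: 22, 17 and 12 days to Day 28; 38, 33 and 28 to Day 44.

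**Fourteen days as a benchmark.** Last active dose plus 14 gives Day 19, 24 and 29, or Day 20, 25 and 30 with the one-day shift. Only the 15-day arm passes Day 28, by one or two days.

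**Pure-delay illustration (assumptions).** Every arm has the same risk r of a rebound-related hospitalization. Onset is uniform over days t = 1 to 14 after the last active dose (day e), and hospitalization follows after a fixed lag of L days. The share captured by horizon H is the number of t with e + t + L ≤ H, divided by 14. The documents give no lag, so a range is shown for H = 28:

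| Lag L (days) | 5-day arm | 10-day arm | 15-day arm |
|---|---|---|---|
| 0 | 100% | 100% | 13/14 = 93% |
| 3 | 100% | 100% | 10/14 = 71% |
| 5 | 100% | 13/14 = 93% | 8/14 = 57% |
| 7 | 100% | 11/14 = 79% | 6/14 = 43% |
| 10 | 13/14 = 93% | 8/14 = 57% | 3/14 = 21% |

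At H = 44 the share is 100% in all arms for every lag shown. With the one-day shift, the no-lag figure in the 15-day arm is 12/14 = 86%.

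**Other shapes.** Suppose time from last active dose to hospitalization follows a gamma distribution with SD 5 days. With mean 14 days, Day 28 captures 95%, 80% and 47%; with mean 10 days, 98%, 93% and 76%. Day 44 captures at least 99% in both cases. Now suppose onset is exponential with median 9 days and L = 7, so that capture = 1 − 2^(−(H−e−L)/9). Day 28 then captures 71%, 57% and 37%, and Day 44 captures 92%, 88% and 82%. The 9-day median is from the retrospective review in Protocol Section 2.2, which does not state the time origin; end of treatment is assumed here. In this case Day 44 shrinks the gap without closing it.

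**Expected Day 28 events** = 50 × r × share captured, 5-day versus 15-day arm:
- r = 0.8%, L = 7: 0.40 versus 0.17.
- r = 5%, L = 5: 2.5 versus 1.4.
- r = 10%, L = 7: 5.0 versus 2.1. The spurious difference is (2.14 − 5.0)/50 = −5.7 percentage points. The 95% half-width is 1.96 × √(0.100×0.900/50 + 0.043×0.957/50), about 10 points.

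For scale, the earlier trial saw 8/1039 = 0.77% hospitalized by Day 28 on the 5-day course, which is about 0.4 of an event in 50 participants. The rate in immunocompromised participants is not given and may be higher.

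**The case against.** A reader might infer that the protocol's own rebound window is still open at Day 28 in the 15-day arm, so that the endpoint contradicts the protocol. The documents do not support this. The text says "The onset of rebound in COVID-19 symptoms must occur within 14 days after the completion of the initial 5-day course of nirmatrelvir/ritonavir", and that is an eligibility rule for the additional population after a 5-day course, not a risk period for the randomized arms. Even as a benchmark it costs the 15-day arm only one or two days. The larger effects above come from an assumed lag to hospitalization.

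A reader might also infer that the plan cannot show postponed events. It can, in part. Any-duration hospitalization includes every stay over 24 hours and is followed to Day 44 at least, and death is followed to Week 24. The cover is incomplete because shorter stays are mixed in, death is analysed separately, and SAP 6.2.11 to 6.2.13 disagree with Appendix 1 on the horizon.

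Nor is it established that Day 28 will favour longer courses; that follows only if they delay events without preventing them. A common horizon from Day 1 is a legitimate description of treatment strategies. No hypothesis is tested, and pairwise differences are specified for the primary endpoint, not for this composite. These points stand and lower the weight of the concern. They do not remove the unequal off-treatment time, which anyone reading the three Day 28 figures side by side will need to know.

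**Conclusion.** The point holds as a minor but worthwhile improvement to one descriptive secondary endpoint. That the composite ends at Day 28, with 23, 18 and 13 off-treatment days, follows directly from the documents. The direction of the distortion is conditional on longer treatment only postponing events, and its size is not known. Under the uniform-onset assumption, the 15-day arm loses 7% of events by Day 28 with no lag and 57% with a seven-day lag, and nothing by Day 44. With few events per arm, the sampling error in the worked 10% case (about 10 points) exceeds the spurious difference (5.7 points). The concern is therefore about how the figures will be read, not about an invalid test.

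**What to change.** In SAP 6.2.9 and Appendix 1:
- Add the same composite (hospitalization for more than 24 hours or death from any cause) through Day 44, with the same Kaplan-Meier method and curves drawn to Day 44.
- Keep Day 28 for comparability with the earlier trial.
- State that Day 28 results read across arms rest on unequal off-treatment time.
- Reconcile SAP 6.2.11 to 6.2.13 (Day 44 and Week 24) with Appendix 1 (Day 44 only).

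No new data are needed. The Schedule of Activities records COVID-19-related medical visits at Days 35 and 44 and Weeks 12 and 24, and Protocol Section 8.2.2 collects admission and discharge dates. The cost is one more table with its curves and some SAP wording. The downside is that a few later deaths from other causes may enter the composite.

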### Overall Design:

This Phase 2, randomized, double-blind study will evaluate the efficacy and safety of nirmatrelvir/ritonavir (5-, 10-, and 15-day dosing durations) for the treatment of COVID-19 in approximately 150 nonhospitalized symptomatic participants aged at least 12 years and weigh  $\geq 40$  kg who are immunocompromised (main study population). In addition, this study will also evaluate the efficacy and safety of a second treatment course of nirmatrelvir/ritonavir (5-, 10-, or 15-days) in an additional population of nonhospitalized symptomatic participants who are immunocompromised with a rebound in COVID-19 within

14 days following completion of an initial 5-day treatment course of nirmatrelvir/ritonavir (population with rebound).

Participants in the additional population with rebound will be recruited during the enrollment phase for the main study population. Enrollment of the population with rebound will stop after the main study population is fully enrolled or after 50 participants in the population with rebound have been enrolled, whichever occurs sooner.

Participants will be screened on the same day as randomization or 1 calendar day before randomization. The total study duration is up to 24 weeks, including study intervention administration through Day 15 or Day 16, safety assessments through Day 44, efficacy assessments through Week 24, and long-term follow-up at Weeks 12 and 24.

An independent E-DMC will review unblinded data to ensure the safety of participants on an ongoing basis throughout the duration of the study.

**Number of Participants:**

Up to approximately 200 participants will be enrolled in this study.

The study will randomize approximately 150 participants in a 1:1:1 randomization ratio, resulting in approximately 50 participants in each treatment arm (main study population). Randomization of the main study population will be stratified by those who are considered immunocompromised solely based on corticosteroids or TNF blocker use (yes/no). Enrollment of participants in the main study population considered immunocompromised based solely on receiving corticosteroids or TNF blockers will be capped at approximately 25%.

In addition, the study will also randomize an additional population of up to 50 nonhospitalized symptomatic participants (in a 1:1:1 randomization ratio) who are immunocompromised with a rebound in COVID-19 within 14 days following completion of an initial 5-day treatment course of nirmatrelvir/ritonavir (population with rebound).

Randomization for the population with rebound will not be stratified by those who are considered immunocompromised solely based on corticosteroids or TNF blocker use. Enrollment of participants considered immunocompromised based solely on receiving corticosteroids or TNF blockers in the additional population with rebound will not be capped.

Note: "Enrolled" means a participant's, or their legally authorized representative's, agreement to participate in a clinical study following completion of the informed consent/assent process and screening. A participant will be considered enrolled if the informed consent/assent is not withdrawn prior to participating in any study activity after screening. Potential participants who are screened for the purpose of determining eligibility for the study, but do not participate in the study, are not considered enrolled.

## **Study Population:**

Key inclusion and exclusion criteria are listed below:

### **Inclusion Criteria**

Participants must meet the following key inclusion criteria to be eligible for enrollment into the study:

1. Participants aged 12 years or older and weighing  $\geq 40$  kg at screening.
  - Refer to protocol for reproductive criteria for female participants.
2. Confirmed SARS-CoV-2 infection as determined by RT-PCR or other acceptable test method in any specimen collected.
3.  $\geq 1$  sign/symptom attributable to COVID-19 present on the day of randomization.
4. Immunocompromised.

### **In addition, the following inclusion criteria only apply to the additional population with rebound:**

5. Presenting with documented, symptomatic, COVID-19 rebound within 14 days following completion of an initial 5-day treatment course with nirmatrelvir/ritonavir.

### **Exclusion Criteria**

Participants with any of the following characteristics/conditions will be excluded:

1. Current need for hospitalization or anticipated need for hospitalization within 24h after randomization in the clinical opinion of the site investigator.
2. Known medical history of active liver disease (other than nonalcoholic hepatic steatosis), including chronic or active hepatitis B or C infection, primary biliary cirrhosis, Child-Pugh Class C, or acute liver failure.
3. History of hypersensitivity or other contraindication to any of the components of the study interventions, as determined by the investigator.
4. Suspected or confirmed concurrent active systemic infection other than COVID-19 that may interfere with the evaluation of response to the study intervention.
5. Any comorbidity requiring hospitalization and/or surgery within 7 days prior to study entry, or that is considered life threatening within 30 days prior to study entry, as determined by the investigator.

6. Receiving dialysis or have known age-specific eGFR <30 mL/min/1.73 m^2 or eCrCl <30 mL/min at screening as measured by a serum creatinine point of care device.
7. Oxygen saturation of <92% on room air obtained at rest within 24h prior to randomization.
8. Other medical or psychiatric condition including recent (within the past year) or active suicidal ideation/behavior or laboratory abnormality that may increase the risk of study participation or, in the investigator's judgment, make the participant inappropriate for the study.
9. Current use of any prohibited concomitant medication(s).
10. Current or previous administration with an investigational product (drug or vaccine) within 30 days (or as determined by the local requirement) or 5 half-lives preceding the first dose of study intervention used in this study (whichever is longer).  
Authorized or products with conditional approval are not considered investigational.
11. Prior participation in this trial.
12. Females who are pregnant up to <14 weeks gestation. Pregnancy ≥14 weeks is not exclusionary.
13. Investigator site staff directly involved in the conduct of the study and their family members, site staff otherwise supervised by the investigator, and sponsor and sponsor delegate employees directly involved in the conduct of the study and their family members.

